Summary	
Radiotherapy can be considered as standard treatment option for patients with low grade glioma. Typically, a dose of 45-54 Gy in conventional fractionation of 1.8-2 Gy is applied. Age of the patient, size and localization of the tumor as well as neurologic status can affect the choice of the appropriate irradiation modality. Irradiation with photons is still the predominantly used modality. Considering that the prognosis is typically favorable the prevention of late sequelae is of particular importance.
 
Proton beam therapy (PRT) and its advantageous physical properties has the potential to further reduce the burden of treatment related side effects. However, in about 20 % of all patients, late contrast-enhancing brain lesions (CEBL) appear on follow-up MR images 6 – 24 months after treatment. At HIT in Heidelberg and at OncoRay in Dresden, CEBLs have been observed to occur at very distinct locations in the brain and treatment field. Retrospective analysis has elucidated potential key factors that lead to CEBL occurrence. However, avoidance of CEBLs is hardly feasible using conventional treatment planning strategies.
 
Model-aided risk avoidance denotes the use of model-based CEBL risk calculations as an auxiliary tool for clinical treatment planning: Model-based risk calculations and risk reduction via software-based optimization help the clinician to minimize risk of CEBL occurrence during treatment planning.
 
In a randomized-controlled trial, patients with low-grade glioma will be treated based on treatment plans that rely on either conventional planning strategies (control arm), or planning with model-aided risk avoidance (interventional arm). Through regular follow-up examinations during a period of at least 24 months post treatment, occurrence of CEBLs will be examined by MR imaging in all patients. The hypothesis will be tested that model-aided risk avoidance reduces the overall incidence of CEBLs.

Principal investigator / Trial Coordinator	[name]
Clinical Trial Office	[name]

Trial population	
inclusion criteria:
 
  Age > 18 years  histologically proven low-grade glioma  indication for definitive or adjuvant radiotherapy  ability to understand character and personal consequences of the clinical trial  written informed consent 
exclusion criteria:
 
  previous cerebral irradiation  contraindication for contrast-enhanced MRI  neurofibromatosis  participation in another clinical trial with competing objectives
Trial design	Multicentric prospective interventional, randomized, observer blind two arm (active control), parallel group investigator-initiated phase II trial with interim analysis to assess feasibility of model-aided optimization of proton beam treatment planning
Sample size	
To be assessed for eligibility: n = 150
 
To be allocated to trial: n = 120
 
To be analyzed: n = 100

Trial treatment	Patients will be randomized to either conventional or model-aided treatment planning arm stratified by center. Both arms receive standard radiotherapy for patients with low grade glioma up to 54 Gy RBE.
Treatment technique	Protons, active raster-scanning, SBO/IMPT, model-guided re-planning
Trial hypotheses	
Model-guided risk avoidance reduces the risk of contrast-enhancing brain lesions in low-grade glioma patients treated with proton-beam therapy.
 
To formalize the statistical approach, the following notation will be used:
 
p_{conv}/p_{aided}: cumulative incidence CEBL negative binomial rate within 24 months in the conventional / model-aided experimental group. The following test problem is defined:
 
$H_0: p_{aided} \geq p_{conv}$ vs. $H_1: p_{aided} < p_{conv}$,
 
which will be assessed at a one-sided significance level of 2.5 %.

Outcome(s)	
Primary endpoint: cumulative incidence of contrast-enhancing brain lesions within 2 years. Contrast-enhancing brain lesions are defined as focal spots diagnosed by contrast-enhanced MRI within or adjacent to the irradiated high dose volume, but outside the initial tumor volume (independently diagnosed by two radiologists).
 
Key secondary endpoint(s): Incidence of radiation-induced brain injuries > CTC^oII, progression-free survival, overall survival, safety.

	Assessment of safety: Safety will be assessed by the type, incidence, severity (graded by the NCT CTCAE Version 5.0) and relatedness of AEs to treatment.
Sample size calculation	
Sample size calculation is based on the primary endpoint “cumulative incidence of contrast enhancing brain lesions (CEBL) observed within 24 months after PRT”.
 
Analyses based on own retrospective data showed that the primary endpoint is negative binomial distributed and that an 86% cumulative incidence CBL rate (of greater or equal than one), p_{conv}, as well as dispersion parameter of $\Phi=0.2597$ can be assumed in the conventional group. On the bases of additional experiments, a 60% reduction of p_{conv} in the model-aided experimental group is assumed, hence $p_{aized}=0.6*p_{conv}$, when assuming the same dispersion parameter in both groups.
 
For a fixed sample size design, the sample size required to achieve a power of $1-\beta$ of 80% for the one-sided negative binomial regression at a significance level of $\alpha=0.025$ assuming the same dispersion-parameter in conventional and experimental group and a randomization allocation ratio of 1:1 as well as the above-mentioned assumptions, amounts to $2*46=92$. It can be expected that including covariates of prognostic importance in the negative binomial regression model as defined for the confirmatory analysis (see Section 9) will increase the power as compared to no included covariates.
 
A group-sequential design with interim analysis allowing to prematurely stop the trial for efficacy or futility (using O’Brien-Fleming- type alpha and beta spending functions) is performed. This will allow to prematurely declare the treatment as effective in case of a substantially large treatment effect, as well as to stop the trial in case the treatment does not prove to be effective. The interim analysis is conducted after half of the patients did reach the primary endpoint. Additionally, the study can be stopped in the interim analysis due to futility. These assumptions would lead to a sample size of 98 (49 per group) without consideration of drop-outs or premature death within 12 months after randomization. With an assumed 18% drop-out rate, 120 patients (60 per group) are needed to achieve a power of 80%. Calculations were performed with R packages gscounts (Mütze et al. 2018) for sample size calculations and MASS (Venables & Ripley 2002) for estimation of the dispersion parameter. R version 4.1.2 was used.

Statistical analysis	Primary Endpoint

The primary endpoint of this clinical trial is the cumulative incidence of CEBLs within 24 months after PRT measured by quarterly contrast enhanced MRI of the brain. The null hypothesis is tested with a two-level negative binomial regression model including the covariates treatment, prescribed dose, and the random factor center at an overall one-sided significance level of $\alpha = 0.025$ is applied. Confirmatory analysis of the primary endpoint will be primarily based on the Full Analysis Set. An evaluation of the per protocol and safety set is performed additionally. Also, multiple sensitivity analyses of the primary endpoint will be performed.

A group-sequential design with interim analysis according to O'Brien-Fleming type alpha and beta spending decision boundaries is performed. The interim analysis is conducted after $n = 49$ patients did reach the primary endpoint within 24 months, which is half of the planned total sample size not considering dropouts or premature deaths. No sample size recalculation is performed at the interim analysis. This design allows early stopping of the trial under control of the overall type I error rate, or, alternatively, a stop for futility. Results of the interim analysis will be presented to the Data Safety and Monitoring Board (DSMB) who will advise the Steering Committee of the trial to either terminate or to continue the trial.

Secondary endpoints

[figure not shown]
The secondary endpoints overall survival and progression-free survival will be analyzed using Kaplan-Meier-Curves. The 1-year and 2-year survival rates as well as the median survival rate will be provided alongside two-sided 95%- confidence intervals. Furthermore, progression-free-survival and overall survival will be descriptively assessed at the interim analysis using Kaplan-Meier curves. A Cox regression frailty model will be conducted to compare the two treatment groups. The other secondary endpoints and the patients' characteristics will be displayed by descriptive measures grouped by treatment group. Continuous variables will be described using number non-missing values, mean, standard deviation, median, Q1, Q3, minimum and maximum. For binary or categorical variables absolute and relative frequencies will be provided.

Safety analysis

For safety analysis, laboratory parameters, all AEs and all SAEs will be analyzed via descriptive statistical methods in the safety population. The

	safety analysis includes calculation of frequencies and rates of complications and serious adverse events together with corresponding 95%-confidence intervals. In addition, tolerability and dosing will be described by numbers of patients in whom treatment was given as planned, delayed or permanently stopped. Detailed procedures of the interim and final analysis will be specified in separate Statistical Analyses Plans (SAP), which will be finalized before interim/final database lock.
Trial duration	Overall duration: 60 months Minimal Follow-up: 24 months FSI (first subject in): 01/2023 50% accrual: 09/2024 LSI (last subject in): 01/2026 LSO (last subject out): 01/2028
Participating sites	University Hospital Heidelberg - HIT University Hospital Dresden - OncoRay

Flowchart

Treatment schedule	baseline visit	weekly during RT	end of RT	FU 1 6 weeks post RT	FU 2 3 months post RT	FU 3 6 months post RT	FU 4 9 months post RT	FU 5 12 months post RT	FU 6 15 months post RT	FU 7 18 months post RT	FU 8 21 months post RT	FU 9 24 months post RT
Informed consent	✓											
Inclusion/exclusion criteria	✓											
Demographic information	✓											
Anamnesis/clinical examination	✓			✓	✓	✓	✓	✓	✓	✓	✓	✓
randomization	✓											
AEs und SAEs	✓	✓	✓	✓	✓	✓	✓	✓	✓	✓	✓	✓
Symptoms/toxicity	✓	✓	✓	✓	✓	✓	✓	✓	✓	✓	✓	✓
MRI	✓			✓	✓	✓	✓	✓	✓	✓	✓	✓
QLQ-C30 & QLQ-BN20	✓		✓			✓		✓				✓
PRO-CTCAE	✓	✓	✓	✓	✓	✓	✓	✓	✓	✓	✓	✓
(Cognitive assessment)	✓		✓			✓		✓				✓

1 Introduction

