1.2 Trial rationale

Since patients with low grade glioma are expected to become long-term survivors, the prevention of long-term sequelae is particularly important. In addition to disease progression, also treatment related side effects such as decline of neurocognitive function, endocrine impairment or sensorineural deficits can have a negative impact on patient's quality of life.

Owing to the biophysical properties of protons with an inverse depth dose profile compared to photons and a steep dose fall off to the normal tissue, there is a strong rationale for the use of PRT in the treatment of patients with low-grade glioma. Although data from large randomized trials are still missing there is increasing evidence from smaller prospective trials and retrospective analyses that the expected advantages indeed transform into clinical advantages [5,6].

However, in about 20 % of all patients, late contrast-enhancing brain lesions (CEBL) appear on follow-up MR images 6 – 24 months after treatment [7]. At HIT in Heidelberg and at OncoRay in Dresden, CEBLs have been observed to occur at very distinct locations in the brain and relative to the treatment field. Retrospective analysis has elucidated potential key factors that lead to CEBL occurrence. However, avoidance of CEBLs is hardly feasible using conventional treatment planning strategies. Model-aided risk avoidance denotes the use of model-based CEBL risk calculations as an auxiliary tool for clinical treatment planning: Model-based risk calculations and risk reduction via software-based optimization help the clinician to minimize risk of CEBL occurrence during treatment planning.

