10.5 Confidentiality

The data obtained in the course of the trial will be treated pursuant to the Federal Data Protection Law (Bundesdatenschutz- bzw. Landesdatenschutzgesetz, BDSG-neu, LDSG and the General Data Protection Regulation (DSGVO).

During the clinical trial, patients will be identified solely by means of their year of birth, and an individual identification code (Subject ID). Trial findings stored on a computer will be stored in accordance with local data protection law and will be handled in strictest confidence. For protection of these data, organizational procedures are implemented to prevent distribution of data to unauthorized persons. The appropriate regulations of local data legislation will be fulfilled in its entirety.

The subject consents in writing to relieve the investigator from his/her professional discretion in so far as to allow inspection of original data for monitoring purposes by health authorities and authorized persons (inspectors, monitors, auditors). Authorized persons (clinical monitors, auditors, inspectors) may inspect the subject-related data collected during the trial ensuring the data protection law.

The investigator will maintain a subject identification list (subject IDs with the corresponding subject names) to enable records to be identified.

Patients who did not consent to circulate their pseudonymized data will not be included into the trial.

11 Sample Size

Sample size calculation is based on the primary endpoint “cumulative incidence of contrast enhancing brain lesions (CEBL) observed within 24 months after PRT”.

Our previous analysis showed that the primary endpoint is negative binomial distributed and that an 86 % cumulative incidence CBL negative binomial event rate, p_{conv} , as well as dispersion parameter of $\Phi = 0.2597$ can be assumed in the conventional group. On the bases of additional experiments, a 60 % reduction of the probability for at least one lesion in the model-aided experimental group is assumed, corresponding to a negative binomial event rate $p_{aided} = 0.18$ when assuming the same dispersion parameter in both groups.

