performed. This will allow to prematurely declare the treatment as effective in case of a substantially large treatment effect, as well as to stop the trial in case the treatment does not prove to be effective. The interim analysis is conducted after half of the patients did reach the primary endpoint (see the detailed description of the procedure applied for the interim analysis in section 13.3 below). Additionally, the study can be stopped in the interim analysis due to futility (boundaries for interim and final analysis are given in section 13.4). These assumptions would lead to a sample size of 98 (49 per group) without consideration of drop-outs. With an assumed 18% drop-out rate 120 patients (60 per group) are needed to achieve a power of 80%.

It should be noted that the interim analysis will likely take place after the total number of 120 patients have been enrolled. While in such a case, it is not possible to reduce the total number of enrolled patients, the follow-up time of the trial might be reduced, thus allowing to save resources and costs.

Calculations were performed with R packages gscounts for sample size calculations and MASS for estimation of the dispersion parameter. R version 3.6.3 was used.

12 Statistical Analyses

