12.2 Hypothesis

To formalize the statistical approach, the following notation will be used:

p_{conv}/p_{aided} : cumulative incidence CEBL negative binomial rate within 24 months in the conventional / model-aided experimental group. The following test problem is defined:

$$H_0: p_{aided} \geq p_{conv} \quad \text{vs.} \quad H_1: p_{aided} < p_{conv},$$

which will be assessed at a one-sided significance level of 2.5 %.

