12.3.2 Confirmatory analysis of the primary endpoint

The null-hypothesis is tested with a two-level negative binomial regression model including the covariates treatment, prescribed dose, and the random factor center. An overall one-sided significance level of $\alpha = 0.025$ is applied. Confirmatory analysis of the primary endpoint will be primarily based on the FAS which is consistent with the intention-to-treat (ITT)-principle by including all patients who were randomized to one of the study

groups. If a patient discontinues from the study prematurely without having a full observation time (e.g. due to death, loss to follow, or withdrawal of informed consent) but was observed for at least one year after randomization, the primary outcome variable will be set to the number of lesions observed until the last available follow-up visit. If a patient has a follow-up less than one year after randomization, the primary endpoint will be set to missing. An evaluation of the PP and safety set is performed additionally and the results are compared with those of the ITT analysis. Additionally, multiple sensitivity analyses of the primary endpoint will be performed by applying alternative methods dealing with missing data such as:

- Complete-case analysis, which means that the primary outcome of all patients with an incomplete 24 month follow up will be set to missing and neglected for the primary analysis.
- Analysis based on the FAS. If a patient discontinues from the study prematurely without having a full observation time, missing data for the primary outcome variable will be replaced by using multiple imputation by means of fully conditional specification method (van Buuren, 2006). The variables treatment, dose, center, lesions observed until censoring, and observation time will be included in the imputation model, which will use predictive mean matching to impute missing primary outcome data.

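### The synopsis and Section 11 attach the same sample size and 80% power to different effects; at the synopsis formula (0.6 times the control rate) power is about 18%

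*Protocol*

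**What the plan says.** The synopsis (Sample size calculation) describes the control parameter as "an 86% cumulative incidence CBL rate (of greater or equal than one", followed by a closing bracket and the symbol for the conventional arm. For the experimental arm it says that "a 60% reduction of p_{conv} in the model-aided experimental group is assumed, hence $p_{aized}=0.6*p_{conv". It then reports 46 per group for a fixed design and 49 per group for the group-sequential design, and concludes: "With an assumed 18% drop-out rate, 120 patients (60 per group) are needed to achieve a power of 80" percent.

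Section 11 (Sample Size) calls the same 86% a negative binomial event rate. It assumes a 60% reduction in the probability of at least one lesion, "corresponding to a negative binomial event rate $p_{aided} = 0.18$ when assuming the same dispersion parameter in both groups". It reports the same 46 and 49 per group and the same conclusion: "With an assumed 18% drop-out rate 120 patients (60 per group) are needed to achieve a power of 80" percent.

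Section 12.2 defines the tested parameter as the "cumulative incidence CEBL negative binomial rate within 24 months in the conventional / model-aided experimental group". Section 12.3.2 sets the test level: "An overall one-sided significance level of $\alpha = 0.025$ is applied". Section 1.2 (Trial rationale) says that "in about 20 % of all patients, late contrast-enhancing brain lesions (CEBL) appear on follow-up MR images 6 – 24 months after treatment".

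**The concern.** Three effects are in play for one sample size:

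- the synopsis words, a 60% reduction of the control parameter, so a rate of 0.4 × 0.86 = 0.344;
- the synopsis formula, 0.6 × 0.86 = 0.516, a 40% reduction;
- Section 11, a rate of 0.18, so a rate ratio of 0.18/0.86 = 0.21, a 79% reduction.

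These cannot all give 80% power with 46 or 49 per group. The synopsis also labels 0.86 as the proportion of patients with one or more lesions, whereas Sections 11 and 12.2 treat it as a rate, that is, a mean count.

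The power claim for the primary endpoint is at stake. Someone relying on the synopsis would believe that the trial has 80% power for a 40% or 60% reduction in the tested rate. A null result or a futility stop would then be read as strong evidence against an effect that the trial was unlikely to detect.

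**Working it through.** **Inputs.** Control mean m0 = 0.86 and dispersion 0.2597 (synopsis, Section 11); one-sided level 0.025 (Section 12.3.2); power 80% and 1:1 allocation (synopsis, Section 11); one interim analysis at half the information, with one-sided p-value boundaries of 0.0015 for efficacy and 0.2879 for futility, and a printed final boundary of 0.0235 (Section 12.4).

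**Reading of 0.2597.** The protocol estimated the dispersion with the R package MASS, whose parameter is the size k, with variance m + m²/k. This reading is tested below against the protocol's own figures.

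**Step 1: Section 11's rate.** The probability of at least one lesion is P = 1 − (k/(k + m))^k.

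- At m = 0.86: 1 − (0.2597/1.1197)^0.2597 = 0.316.
- A 60% reduction gives 0.4 × 0.316 = 0.126, which corresponds to m = 0.177, the stated 0.18 after rounding.
- At m = 0.18 exactly, P = 0.128.

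**Step 2: fixed-design sample size.** For the Wald test of the log rate ratio,

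n per group = (1.96 + 0.8416)² × (1/m0 + 1/m1 + 2/k) / ln(m1/m0)²,

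with (1.96 + 0.8416)² = 7.849 and 2/k = 7.701.

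| m1 | Source | Sum in bracket | ln(m1/m0)² | n per group |
|---|---|---|---|---|
| 0.18 | Section 11 | 14.42 | 2.446 | 46.3 |
| 0.344 | synopsis words | 11.77 | 0.840 | 110 |
| 0.516 | synopsis formula | 10.80 | 0.261 | 325 |

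Section 11 reproduces the stated 46 (45.6 with the unrounded 0.177). Allowing for the interim analysis with futility multiplies n by 1.056, giving 48.2 to 48.9 per group against the stated 49, and 98/(1 − 0.18) = 119.5, so 120.

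**Step 3: the other reading of 0.2597.** With variance m + 0.2597m², the same formula gives 23, 43 and 109 per group for the three effects. None is 46, and the 60% reduction in P would then lead to a mean of 0.25, not 0.18. The size reading is the only one tried that returns both 46 and 0.18.

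**Step 4: group-sequential power at 49 per group.** The interim and final statistics were treated as bivariate normal with correlation √0.5 and the futility rule applied. Power is shown for the printed final boundary and for 0.0245, the nominal level that an O'Brien-Fleming-type spending function yields here.

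| m1 | Rate ratio | Final p 0.0245 | Final p 0.0235 |
|---|---|---|---|
| 0.18 | 0.21 | 80.1% | 79.7% |
| 0.344 | 0.40 | 44% | 43.6% |
| 0.516 | 0.60 | 18.0% | 17.6% |

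If the non-binding futility rule is ignored, power at 0.516 is 18.6% to 19.1%. A simulation of the fixed design with fitted negative binomial models (1,500 runs, 46 per group) gave 82% at 0.18, 44% at 0.344 and 18.4% at 0.516. Even if all 60 per group were evaluable, fixed-design power would be 54% at 0.344 and 22% at 0.516.

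**Step 5: the synopsis label of 0.86.** For 86% of patients to have a lesion at k = 0.2597, the mean would have to be 0.2597 × (0.14^(−1/0.2597) − 1), about 504 lesions per patient. The 0.86 is therefore the mean count, equivalent to 31.6% of patients affected.

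**Step 6 (secondary): the 20% of Section 1.2.** If control incidence were 20% and fell by 60% to 8%, and the same k is assumed, the means would be 0.354 and 0.098. Power would be about 48% and a fixed design would need about 99 per group.

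**The case against.** The strongest reply is that Section 11 is coherent and reproduces 46, 49 and 120, so the synopsis line is only a faulty condensation of it. On that view nobody planned for a rate of 0.516, and the 18% describes an accidental formula. This stands in part: the sample size is supported and need not change. But the slip is more than a wrong digit. Replacing 0.6 by 0.4 still leaves an effect that needs 110 per group. Applying 0.6 to the proportion affected (mean 0.323) gives only 48% power at 46 per group.

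It is also fair that Section 11 prints both rates, so the ratio of 0.21 is one division away. Neither section states that ratio, although the rate is the tested parameter and the only reduction quoted is 60%.

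The comparison of 20% with 31.6% is weaker. The 20% is cited from a reference and refers to lesions appearing at 6 to 24 months; the 0.86 comes from the investigators' retrospective data. The protocol does not show that cohort, window and imaging schedule agree, and the 31.6% comes from a fitted distribution. The main point does not depend on it. Reporting power at further effect sizes is likewise useful but not required.

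**Conclusion.** The concern holds. The synopsis states a planning effect that is internally inconsistent, differs from Section 11, and does not support the power attached to it. The 80% belongs to a rate ratio of 0.21. At the synopsis formula the power is about 18%, and at a true 60% rate reduction about 44%. These figures rest on reading p as the negative binomial mean, as Section 12.2 defines it, and 0.2597 as the size parameter, the only reading tried that reproduces the protocol's own numbers. The choice between 0.0235 and 0.0245 for the final boundary, or ignoring futility, moves the 18% by about one percentage point at most. Because the error concerns the power claim for the primary endpoint, it must be corrected; the planned size and the analysis are unaffected.

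**What to change.** - Replace the synopsis sentence so that it agrees with Section 11: control mean 0.86 lesions per patient in 24 months (31.6% with at least one lesion), model-aided mean 0.18 (12.8%), rate ratio 0.21. Delete the 0.6 formula and the description of 0.86 as the share with one or more lesions.
- In both places, label 0.2597 as the size parameter, with variance m + m²/0.2597.
- State that the 60% refers to the proportion of patients affected, and that 80% power applies to a 79% reduction in the tested rate. Preferably add the power at rate ratios 0.4 (about 44%) and 0.6 (about 18%).
- Add a sentence explaining how the 31.6% implied for controls relates to the 20% in Section 1.2.

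The cost is wording in the synopsis and Section 11, with no change in sample size. The stated power will look less favourable for moderate effects.
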